1.2. Covid-19 positive test measurement

Concept ID	Concept name
37310282	2019 novel coronavirus detected

1.3. Covid-19 (positive or negative) test measurement

Concept ID	Concept name
756055	Measurement of Severe acute respiratory syndrome coronavirus 2 (SARS-CoV-2)
37310281	2019 novel coronavirus not detected
756055	Measurement of Severe acute respiratory syndrome coronavirus 2 (SARS-CoV-2)
37310282	2019 novel coronavirus detected

2. Covid-19 Symptoms

2.1. Fever episodes

Concept ID	Concept name
4329518	Body temperature taken with digital thermometer
4174894	Core body temperature
4212763	Forehead temperature

44809208	Maximum body temperature
4039793	O/E - level of fever
4077057	O/E - oral temperature
4039791	O/E - rectal temperature
4151775	O/E - tympanic temperature
4265708	Temperature of skin
444413	Febrile convulsion
437663	Fever
4141062	Fever greater than 100.4 Fahrenheit
4152360	O/E - fever

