7.3.1. COVID-19 diagnosis

The definitions used for COVID-19 diagnosis will depend on the data source, for example, the primary care data sources usually do not contain the laboratory values. All the analyses will be run on the main definition while the alternative definitions will be used for secondary objective 4 - to explore how COVID-19 is captured across different databases. (see Appendix 1 for code lists)

1. Catch-all (main definition, the most sensitive)

¹ Cardiovascular disease as a subgroup variable has a different definition from the composite cardiovascular event as an adverse event which is focused on acute and severe outcomes.

Defined either as the first confirmed diagnosis for COVID-19 **OR** the first SARS-CoV-2 positive PCR test, if both present the earliest date will be considered.

Alternative definitions

2. Diagnosis confirmed (diagCOVID-19)

Defined as one of the following medical codes for COVID-19 at any time (first occurrence considered):

- U07.1 COVID-19, virus identified
- U07.2 COVID-19, virus not identified

3. Laboratory confirmed (labCOVID-19)

Defined as a record of SARS-CoV-2 positive PCR as performed on nasopharyngeal swabs and/or on respiratory tract secretions and aspirates.

We will not include the testing for the presence of antibodies due to the issue of not knowing the point of infection via antibody testing. If patient has more than one test, first occurrence will be considered

4. Symptomatic COVID-19.

At least two symptoms of the following

- Cough
- Dyspnoea
- Fever, unspecified
- Malaise and fatigue
- Myalgia
- Anosmia, Hyposmia or Dysgeusia episodes

5. Suspected COVID-19

- Coronavirus as the cause of diseases classified to other chapters
- Coronavirus infection, unspecified site
- Other viral pneumonia
- Acute bronchitis due to other specified organisms
- Unspecified acute lower respiratory infection
- Bronchitis, not specified as acute or chronic
- Adult respiratory distress syndrome
- Other specified respiratory disorders
- Special screening examination for other viral diseases
- Contact with and exposure to other communicable diseases

This classification is aligned with the ICD-10 International coding guidance on COVID-19 disease (20)

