Appendix 1 Example of code lists

This appendix provides an overview of the standard concepts and cohort set descriptions that are used to define each indication or risk group. The concept ID refers to the unique ID in the OMOP Common Data Model.

1. Covid-19 diagnosis

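### The fever code list includes temperature measurements with no value condition, and the two-symptom rule for symptomatic COVID-19 sets no interval between the symptoms

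*Protocol*

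**What the plan says.** Protocol section 7.3.1 lists five COVID-19 definitions and refers to Appendix 1 for the code lists. Definition 4, symptomatic COVID-19, requires "At least two symptoms of the following" and then names six symptoms. Fever appears there as "Fever, unspecified". The rule gives no interval between the two symptoms and no date to which they are anchored.

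Appendix 1 is headed "Example of code lists". Its opening text describes the contents as "standard concepts and cohort set descriptions that are used to define each indication or risk group". Under 2.1, the fever list includes "Body temperature taken with digital thermometer", "Core body temperature" and "Temperature of skin", together with forehead, maximum, oral, rectal and tympanic temperature. It also includes coded fever findings, one of which is "Fever greater than 100.4 Fahrenheit". No value condition is attached to any measurement entry.

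Section 7.3.1 restricts the alternative definitions to secondary objective 4 and runs all other analyses on the catch-all definition. Section 6.3 separately plans, under secondary objective 1, to describe the number and type of symptoms up to and on the diagnosis date where they are captured, and the time from symptom onset to diagnosis.

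**The concern.** A temperature measurement concept records that a temperature was taken. Without a value condition it does not show that the patient was febrile. Section 7.3.1 names a finding, while the list meant to implement it consists mostly of measurements, so the two do not match.

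The missing interval adds to this. A normal oral temperature in one month and a record of cough or muscle pain many months later would together meet definition 4, although they show neither fever nor a single illness.

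Secondary objective 4 asks how each coding definition performs and how it changes the size of the cohort. If definition 4 is inflated by the code list, the report would present part of a coding artefact as the price of using a broad symptom-based definition. In secondary objective 1, normal readings would add to the fever counts. If symptom onset is taken from the same records, they could also place the onset too early.

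**Working it through.** The protocol gives no figure for this definition, so there is none to reproduce. The check is a count of the list, a reading of the text, and one illustration under assumed rates.

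**1. Composition of the fever list (Appendix 1, 2.1).**
- Temperature measurements without a value condition: digital thermometer, core, forehead, maximum, oral, rectal, tympanic, skin = 8.
- Examination entry for level of fever, which could be read either way = 1.
- Fever or febrile findings: febrile convulsion, fever, fever above 100.4 F, fever on examination = 4.
- Total 8 + 1 + 4 = 13. Only one entry carries a threshold, and it does so in its own name. Nothing applies that threshold to the eight measurements.

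**2. Whether the appendix separates a test from its result elsewhere.** For SARS-CoV-2 tests it does: list 1.2 holds the positive result only, and list 1.3 holds tests with either result. There is no such split for temperature.

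**3. Longest gap allowed between the two symptoms.** Definition 4 is silent on timing, so the only outer bound is the study period in section 7.2.1, from 1 January 2020 to 1 January 2021 at the latest: 366 days. Other rules in the protocol do state windows: 2 days before to 30 days after diagnosis for starting a glucocorticoid (7.3.2.1), and 30 and 120 days in the eligibility criteria (7.2.2.1).

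**4. Where definition 4 and the fever list are used.**
- Definition 4: secondary objective 4 only (7.3.1, 7.7.6), which reports sensitivity, specificity, positive and negative predictive value, and a 5 by 5 matrix across definitions.
- Fever list: definition 4, and the symptom description in secondary objective 1 (6.3, 7.7.3). The two-symptom rule plays no part in secondary objective 1.
- Catch-all cohort, primary objective, incidence analyses: neither is used.

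**5. Illustration of the missing window (all rates are assumptions).** Suppose a person without COVID-19 has temperature readings at rate a and records of one unrelated listed symptom at rate b per study year, independently and at random times. With no window,

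P(both recorded) = (1 − e^−a)(1 − e^−b).

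The probability that some pair falls within 14 days was simulated with 400,000 persons per setting. The 14 days are also an assumption.

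| a | b | No window | 14-day window | Ratio |
|---|---|---|---|---|
| 0.1 | 0.05 | 0.46% | 0.034% | 13.8 |
| 0.3 | 0.2 | 4.70% | 0.425% | 11.0 |
| 1.0 | 0.2 | 11.46% | 1.449% | 7.9 |

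First row: (1 − e^−0.1)(1 − e^−0.05) = 0.0952 × 0.0488 = 0.0046. Over all six settings run, the range was 0.46% to 11.46% without a window and 0.034% to 1.449% with one, a ratio of about 8 to 14. This shows that a second symptom is a weak filter when no interval is set. It does not estimate what these databases would show.

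**The case against.** The strongest reply is that a concept list is not a cohort rule. The appendix is presented as examples, and its lists carry no value, date or count logic for any variable. It puts a non-smoker concept under smoker (5.8) and body weight under obesity (5.7), although section 7.3.5 says obesity comes from diagnosis codes. So not every list can mean that any record makes a case, and value conditions and windows may sit in a cohort specification or analysis plan that is not shown.

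This lowers certainty but does not cure the text. The appendix also says its concepts are used to define each indication, section 7.3.1 sends the reader there, and no passage states a temperature cut-off or defers one to another document. The smoking and obesity lists are as easily read as having the same fault.

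A second reply is that secondary objective 4 exists to expose weak definitions, so a non-specific one would show up as low specificity or predictive value. That is true, but the result would not separate a weak symptom definition from a wrong code list.

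A third reply, that a temperature record alone never qualifies because a second, different symptom is needed, is correct and limits the effect.

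Some stronger readings are tempting but not supported:
- A reader might infer that nearly every hospital patient would count as febrile. Section 7.4 describes the hospital database as holding admissions, conditions, procedures, medicines, discharge and death, and mentions no temperatures. That source has about 2,000 of 153,759 patients (1.3%).
- A reader might take a share of false fever records, such as 70% to 90%, from an assumed 10% to 30% of readings being febrile. That is only one minus the assumption, and it concerns records, not patients meeting definition 4.
- A reader might think definition 4 explicitly accepts symptoms at any time. That wording belongs to definition 2. Definition 4 is silent.

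**Conclusion.** The point holds in a limited form. As written, eight of the 13 fever concepts count a temperature reading as fever whatever its value, and definition 4 allows its two symptoms to lie up to 366 days apart. What is affected is the size, sensitivity, specificity, predictive values and overlap matrix of definition 4 in secondary objective 4 and, through the fever list alone, the symptom description in secondary objective 1.

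It would be wrong to infer that the study cohorts or the main results are contaminated, because they rest on the catch-all definition. The extent of the misclassification cannot be derived from the documents: they do not say which databases hold temperature measurements, how often, or with what values. The conclusion assumes that the printed list is applied as it stands. If an unseen specification already holds a cut-off and a window, only the protocol text needs correcting. This should be settled before the cohorts for secondary objective 4 are built.

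**What to change.** In Appendix 1, 2.1, remove the eight measurement concepts, or keep them only where a recorded value exceeds a prespecified cut-off, stated by measurement site if the study team considers that necessary. Say how the level-of-fever entry is to be read. In section 7.3.1, require the two symptoms of definition 4 to fall within a prespecified window inside the study period, and say which of the two dates is the case date. The study team should choose the cut-off and the window, since the documents supply neither.

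The cost is one concept-set edit and one date condition in the cohort code. Readings stored without a value are lost as evidence of fever, so true fevers recorded only in that way would be missed. Reporting how many such readings each database holds would show whether this matters.

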2.2. Cough

Concept ID	Concept name
254761	Cough
4089228	Sputum finding

2.3. Myalgia

Concept ID	Concept name
442752	Muscle pain

2.4. Malaise or fatigue

Concept ID	Concept name
4223659	Fatigue
4272240	Malaise
439926	Malaise and fatigue

2.5. Dyspnea

Concept ID	Concept name
4191650	Acute respiratory distress
312437	Dyspnea

2.6 Anosmia, hyposmia and dysgeusia episodes

Concept ID	Concept name
43530714	Sensory disorder of smell and/or taste
4185711	Loss of sense of smell
436235	Taste sense altered

3. Adverse events for steroids

3.1. Bacterial infections

Concept ID	Concept name
432545	Bacterial infectious disease
4200533	Bacterial infection by site
438064	Bacterial infection due to Pseudomonas
436339	Bacterial infection due to Klebsiella pneumoniae
4323342	Recurrent bacterial infection
4347525	Disseminated atypical mycobacterial infection
4141201	Beta lactam resistant bacterial infection
4008721	Atypical mycobacterial infection
46274040	History of bacterial infection
42872408	Atypical mycobacterial infection of lung
4029803	Bacterial infection of skin
4215457	Bacterial infection due to Serratia
4094504	Bacterial infection due to Proteus mirabilis
4009326	Mycobacterial infection
4027415	Bacterial infection due to Morganella morganii
438341	Bacterial infection due to Bacillus
46269700	Pleural effusion due to bacterial infection
45768744	Angular cheilitis due to bacterial infection
4193874	Bacterial infection of the digestive tract
37017103	Bursitis caused by bacterial infection
4174693	Atypical mycobacterial infection of hand
4027381	Bacterial infection of central nervous system
4231982	Mycobacterial infection of the central nervous system
46273201	Bacterial infection due to Streptococcus milleri group
37394468	Extended spectrum beta-lactamase resistant bacterial infection
37108786	Herpes zoster with secondary bacterial infection
45770039	SINBAD (site, ischemia, neuropathy, bacterial infection and depth) wound classification
4345453	Skin and soft tissue atypical mycobacterial infection

3.2. Fungal infections

Concept ID	Concept name
4207190	Fungal infection by site
4270197	Fungal infection of lung
4165570	Fungal infection of brain

4030507	Fungal infection of kidney
36717290	Invasive fungal infection

3.3. Pneumonia

Concept ID	Concept name
4050869	Atypical pneumonia
255848	Pneumonia

3.4. Hyperglycemia

Concept ID	Concept name
4214376	Hyperglycemia

3.5. Gastrointestinal bleeding

Concept ID	Concept name
4147683	Acute gastrojejunal ulcer without hemorrhage AND without perforation
40482685	Angiodysplasia of duodenum
28779	Bleeding esophageal varices
198798	Dieulafoy's vascular malformation
4198381	Ulcer of duodenum
4112183	Esophageal varices with bleeding, associated with another disorder
4265600	Gastric ulcer
192671	Gastrointestinal hemorrhage
4027663	Peptic ulcer

3.6. Composite cardiovascular disease events (ischemic stroke, hemorrhagic stroke, heart failure, acute myocardial infarction or sudden cardiac death)

Concept ID	Concept name
4329847	Myocardial infarction
316139	Heart failure
376713	Cerebral hemorrhage
439847	Intracranial hemorrhage
43530674	Spontaneous cerebellar hemorrhage
43530727	Spontaneous cerebral hemorrhage
42535425	Spontaneous hemorrhage of cerebral hemisphere
4148906	Spontaneous subarachnoid hemorrhage
432923	Subarachnoid hemorrhage
372924	Cerebral artery occlusion
375557	Cerebral embolism

443454	Cerebral infarction
441874	Cerebral thrombosis
4048809	Brainstem death
321042	Cardiac arrest
442289	Death in less than 24 hours from onset of symptoms
4317150	Sudden cardiac death
4132309	Sudden death

4. Disease outcomes

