6.3 Secondary Objectives

1. To describe **at COVID-19 diagnosis date and at treatment index date** the demographic, health and clinical patient characteristics. The following variables will be described:
 - demographics
 - comorbidities (number and type)
 - symptoms (number and type) preceding and/or on the date of diagnosis the diagnosis if captured time from onset of COVID-19 illness symptoms to confirmed diagnosis date.

Some of these characteristics will be stratified by setting, glucocorticoid exposure type (naive, prevalent) and subgroups of special interest. (e.g., chronic cardiac and pulmonary disease, diabetes, renal insufficiency, see Section 7.2.4 Subgroups).

2. To quantify the crude and adjusted (selected confounders tbc) incidence rates and time to onset of adverse events of interest (e.g., infections, hyperglycaemia, hypertension, GI bleeding, composite of cardiovascular events) within **30 and 90 days post treatment index date**, in **various treatment groups**, stratified by setting, glucocorticoid exposure type (naive, prevalent) and subgroups of special interest.

3. To quantify the crude and adjusted incidence rates of mortality and other disease outcomes within **30 and 90 days post treatment index date**, in **various treatment groups**, stratified by setting, glucocorticoid exposure type (naive, prevalent) and subgroups of special interest.

4. To explore the performance of **different coding definitions** for COVID-19 and how they influence the size of the cohort

Out of scope:

To assess comparative effectiveness and safety between individual treatments administered for COVID-19 infection or between treated and untreated patients.

To validate definition for COVID-19 using clinical adjudication of individual patient medical records sampled from the study population

[figure not shown]
Section 7.0 Research Methods

[figure not shown]
[figure not shown]

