7.3 Variables

Each treatment/variable definition will be based on standard concepts in the OMOP Standardized Vocabularies. Variables will be identified using pre-specified concept sets reviewed by a core team of clinicians, epidemiologists, vocabulary experts, and health data scientists with extensive expertise in the use of the OMOP CDM and the OHDSI tools. Some of the codes used and validated before will be reused in this project.

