7.3.5 Other Variables

Age – measured both as continuous and categorical variable in years. The following categories will be created:

- <18
- ≥18 and <65
- ≥ 65 and <75
- ≥75

Sex

- Male
- Female

Index month of diagnosis

Comorbidities

- Hypertension
- Type 2 diabetes mellitus
- Chronic obstructive pulmonary disease (COPD)
- Asthma
- Chronic kidney disease
- Ischemic stroke or haemorrhagic stroke
- Heart failure
- Acute myocardial infarction
- Arrhythmia

- Venous thromboembolism (VTE) or pulmonary embolism (PE)
- Obesity (using diagnosis codes)
- Smoker
- Alcohol/Drug abuse
- Autoimmune conditions (type 1 diabetes mellitus, rheumatoid arthritis, psoriasis, psoriatic arthritis, multiple sclerosis, systemic lupus erythematosus, Addisons, Graves, Sjogrens, Hashimoto, myasthenia gravis, autoimmune vasculitis, pernicious anaemia, celiac disease, scleroderma, sarcoid, ulcerative colitis, Crohn disease)
- Organ transplantation,
- Cancer
- Dementia,
- Major psychiatric disorder

These will be used to describe the cohorts at relevant index dates(s) and some of these will be selected as risk factors/confounders for the incidence rates analysis, see section 7.7 for details.

Respiratory support

Patients will be considered having adjunctive respiratory support if available medical records data are available for the following interventions on or post COVID-19 diagnosis:

- Any type of respiratory support
- Invasive mechanical ventilation (including ECMO)
- ECMO only

If no records are observed, then the patient will be considered as receiving no respiratory support.

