4.4. Invasive mechanical ventilation

Concept ID	Concept name
4230167	Artificial respiration
40481547	Dependence on ventilator
4080957	Endotracheal respiratory assistance
4168966	Endotracheal tube present
4232550	Home visit for mechanical ventilation care
4235361	Hyperventilation therapy for traumatic brain injury
37116689	Insertion of endotracheal ventilation catheter
40487536	Intubation of respiratory tract
4332501	Management of noninvasive mechanical ventilation
37206832	Mechanical insufflation exsufflation
765576	Orotracheal intubation using bougie device
4219858	Problem with patient ventilator
2788037	Respiratory Ventilation, 24-96 Consecutive Hours
2788038	Respiratory Ventilation, Greater than 96 Consecutive Hours
2788036	Respiratory Ventilation, Less than 24 Consecutive Hours
4237618	Ventilator care
4251737	Ventilator care management
44791135	Ventilatory support
4072633	Weaning from mechanically assisted ventilation

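### Applied as printed, several Appendix 1 code lists would misclassify patients, because they hold concepts that contradict their own heading

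*Protocol*

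**What the plan says.** The introduction to Protocol Appendix 1 calls its contents the "standard concepts and cohort set descriptions that are used to define each indication or risk group". The appendix itself is headed "Example of code lists". Section 7.3 adds: "Variables will be identified using pre-specified concept sets reviewed by a core team of clinicians". Section 7.3.1 refers the reader to Appendix 1 for the COVID-19 code lists. The tables have two columns, concept ID and concept name, with no inclusion or exclusion mark and no value limit.

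The entries in question are:

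- List 3.5, Gastrointestinal bleeding, includes "Acute gastrojejunal ulcer without hemorrhage AND without perforation" (4147683).
- Lists 4.4, Invasive mechanical ventilation, and 6.2, Invasive respiratory support, both include "Management of noninvasive mechanical ventilation" (4332501). List 6.1, Noninvasive respiratory support, holds one concept, oxygen therapy.
- List 3.1, Bacterial infections, under the adverse events heading, includes "History of bacterial infection" (46274040) and the SINBAD wound classification (45770039).
- List 5.8, Smoker, has two concepts: smoker and non-smoker (4222303).
- List 5.7, Obesity, includes body weight (4099154) without a cut-off, while section 7.3.5 has "Obesity (using diagnosis codes".

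These lists feed stated objectives. Section 6.3 gives the adverse events of secondary objective 2 as "infections, hyperglycaemia, hypertension, GI bleeding, composite of cardiovascular events". Section 6.2 lists invasive and non-invasive respiratory support during follow-up among the variables of the primary objective. Section 7.3.5 uses smoking and obesity to describe the cohorts and says that some of the comorbidities will be selected as confounders.

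**The concern.** A concept set normally works as an any-of rule: one matching record makes the patient a case. Read that way, a patient coded with an ulcer and explicitly no haemorrhage becomes a GI bleeding event. A patient on non-invasive ventilation is counted as invasively ventilated and cannot be counted as non-invasive. A note of a past infection made after treatment starts becomes a new infection. A recorded non-smoker becomes a smoker, and anyone who has been weighed becomes obese.

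The lists need to be right before extraction. Under section 8.0 the analyses run locally and only aggregate results leave each site, so misclassified patients could not be separated afterwards from the central output. Section 7.2.1 says the results will not be refreshed after extraction.

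**Working it through.** The plan states no figure to reproduce. The check sets each list against its heading and the body text, with a hand count of concepts.

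| List | Concepts printed | At odds with heading | Left after correction |
|---|---|---|---|
| 3.5 Gastrointestinal bleeding | 9 | 1 excludes haemorrhage; 5 more do not name bleeding | 9 − 1 = 8, or 9 − 6 = 3 if bleeding must be named |
| 4.4 Invasive mechanical ventilation | 19 | 1 | 18 |
| 6.2 Invasive respiratory support | 29 | 1 | 28 |
| 6.1 Noninvasive respiratory support | 1 | 0 | 2, with 4332501 moved in |
| 5.8 Smoker | 2 | 1 | 1 |
| 5.7 Obesity | 7 | 1 | 6 |
| 3.1 Bacterial infections | 28 | 2 | 26 |

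**GI bleeding.** Three concepts name bleeding or haemorrhage: 28779, 4112183 and 192671. The other six are the ulcer quoted above, gastric ulcer, duodenal ulcer, peptic ulcer, duodenal angiodysplasia and Dieulafoy's malformation. Section 7.3.3 puts gastritis, gastric ulcer and GI bleed in one bullet, so the list might be meant for that combined outcome. It does not implement that either, since it has no gastritis concept. As printed it matches neither GI bleeding in section 6.3 nor the combined bullet in 7.3.3.

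**Respiratory support.** Concept 4332501 is the only one across lists 4.4, 6.1 and 6.2 whose name says non-invasive ventilation, and it sits in both invasive lists. It also appears in list 4.3, Intensive services, whose heading does not say invasive, so there is no contradiction there.

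**Smoker.** Let p be the true share of smokers, all recorded as such, and r the share of non-smokers with a non-smoker record. The list as printed flags p + (1 − p) × r instead of p. The excess, (1 − p) × r, is positive whenever any non-smoker is recorded. Neither p nor r is in the documents, so the direction is known and the size is not.

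**Obesity.** Under an any-of reading one body weight record suffices. A weight measurement is not a diagnosis code, so the entry conflicts with 7.3.5 unless a value limit exists that is not printed, and even then it would not be a diagnosis code.

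**Bacterial infection.** Section 7.3.3 introduces its list as acute adverse events, and section 7.7.4 counts incident events. A history code describes a past event, and SINBAD is a wound grading scheme; neither identifies a new infection.

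**The case against.** The strongest reply concerns the status of the lists. They are headed as examples, the executable concept sets are not shown, and section 7.3 commits to clinical review of them. Some printed lists cannot be plain any-of rules: the fever list (2.1) contains bare temperature measurements that make sense only with a threshold, and list 1.3 places detected and not-detected results together and prints concept 756055 twice. Body weight may likewise carry an unprinted limit, and smoker and non-smoker may be two levels of one status variable. This stands, and it makes the point conditional. It does not remove it: the appendix says the concepts define the groups, and if flags or limits exist, the printed lists misdescribe the definitions.

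The single bullet in 7.3.3 also means that ulcer codes are not foreign to the plan. Five of the six non-bleeding entries are therefore partly a labelling matter; an ulcer with haemorrhage excluded cannot count as bleeding under any label.

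The reach is limited too. Glucocorticoid use is defined by ATC codes in 7.3.2.1 and is untouched. The respiratory support categories in 7.3.5 include no separate non-invasive class, although 6.2 and 7.7.2 do refer to non-invasive support. The primary confounding adjustment in 7.7.5 is a propensity score on the standard OHDSI covariates, so misdefined smoking or obesity would enter only the predefined-confounder model, and only if selected.

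A reader might infer that the reported events and characteristics are wrong, or put a prevalence on the smoking error. The documents support neither. No results exist, the lists that will be run are not shown, and any such percentage would rest wholly on assumed smoking and recording rates.

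**Conclusion.** The contradictions are on the face of Appendix 1. If the lists are applied as printed, GI bleeding and bacterial infection events, the invasive/non-invasive support variable of the primary objective, and smoking and obesity would be misclassified. In concept counts, one of nine GI bleeding concepts excludes haemorrhage and six do not name it. One concept of 19 and one of 29 in the invasive lists is non-invasive. One of two smoker concepts is the opposite state, one of seven obesity concepts is an unbounded measurement, and two of 28 bacterial infection concepts are not acute infections. Counts of concepts are not counts of patients; without code frequencies, the effect on rates or prevalences cannot be derived. The conclusion assumes any-of matching with no unprinted exclusions or limits. If those exist, what remains is a correction to the printed definitions. Either way the correction is due before extraction.

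**What to change.** Edit the lists before extraction:

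- **3.5:** either restrict GI bleeding to haemorrhage concepts and report gastritis and ulcer separately, splitting the single bullet in 7.3.3; or relabel the list as the combined outcome of 7.3.3 and add the missing gastritis concepts. In neither case count 4147683 as bleeding.
- **4.4 and 6.2:** move 4332501 to list 6.1.
- **3.1:** delete 46274040 and 45770039.
- **5.8:** delete 4222303 from the case-defining list.
- **5.7:** delete 4099154, to match 7.3.5.
- **All lists:** print any exclusion flags and value limits that apply in the executable sets.

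The cost is a concept-set edit and a matching text change, made once before the code is run across the eight databases. Under the first option for list 3.5 there will be fewer GI bleeding events and less precise rates, since bleeding coded only under a general ulcer concept would be lost.
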